- 5) To explore the effects of an early literacy promotion program compared to standard literacy promotion on social-emotional development among poor urban children in Philadelphia.

Study Design:

A randomized controlled trial will be conducted comparing two versions of the parent-child reading program: Early literacy promotion (ELP) and Standard Literacy promotion (SLP). An additional sub-study will utilize semi-structured interviews with a purposive number of parents enrolled in the study to explore barriers and promoters to reading to their children.

Setting/Participants:

We will recruit participants who are English or Spanish speakers, at least 15 years old, the parent of a child born ≥ 35 weeks gestation age and < 4 weeks at enrollment and with Medicaid insurance. We will be recruiting from one urban site affiliated with CHOP (Karabots). The combined total enrollment number of participants will be 240 (120 dyads of parent and infant). The target enrollment number of participants for the sub-study will be up to 30 parents.

Study Interventions and Measures:

In this intervention, parents/children randomized to the ELP arm will receive a book with developmentally appropriate advice about reading at each well child visit from one week through 5 months of age, as well as weekly text reminders related to reading. Those in the SLP arm will receive weekly text messages about child safety. From 6 months of age, both groups will receive SLP and will attend study visits every six months until age 2. Difference between the groups on the PLS (Pre-school language score-5th edition) score at 6 and 24 months of age are the main outcomes. StimQ score differences at 6,12,18, and 24 months of age will be a secondary outcome. Other outcomes include score differences at 12, 18, and 24 months in the PHQ-9 and the PSI-Short Form, and differences in the ITSEA at 18 and 24 months. A purposive sample of parents will participate in a qualitative interview component to understand barriers to reading, parents' perceptions of the value of reading to infants, and factors which promote reading.

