3 INVESTIGATIONAL PLAN

3.1 General Schema of Study Design

We propose to test the effects of early literacy promotion using a randomized controlled trial design. Eligible newborn children less than 1 month of age who present to Karabots Primary Care Center will be recruited and consented to participate in this two-year study. Children will be randomized to receive early literacy promotion or standard literacy promotion. Randomization sequences will be developed by the project biostatistician using computer-generated random numbers prior to study enrollment and will be placed in sealed opaque envelopes. Randomization will ensure equivalence between groups on measured and unmeasured characteristics and is considered to be the strongest protection against bias in study design.

Children randomized to the early literacy promotion arm will receive developmentally appropriate books and information on the importance of early parent-child reading activity by pediatric clinicians at well child visits from one week to 6 months of age, and weekly text message reminders concerning early literacy and daily reading activity up to 6 months of age. Developmentally appropriate books will be selected and standardized for each well child visit prior to 6 months of age (1 week, 1 month, 2 months, 4 months). Information on early literacy promotion will be standardized using a verbal script (Appendix 8) and will be provided to parents by pediatric clinicians at well visits prior to 6 months of age. The weekly text message reminders will be initiated following enrollment, will be standardized according to age, and will be scheduled according to parent preference in the morning, afternoon, or evening. The text message reminders will help remind parents to ensure that children in the intervention arm are exposed to parent-child reading activity in their first six months of life. Beginning with the 6-month well child visit, children in this arm will receive the standard ROR Program as described in the standard literacy promotion group below.

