 - Parents will complete measures of reading activity (Stim-Q) at each study visit.
 - Children will complete measure of child expressive and receptive language development (Preschool Language Scale-V) at 6- and 24-month visits.
 - At the 12-, 18-, and 24-month visits, parents will complete the PSI and PHQ-9 questionnaires.
 - At the 18- and 24-month visits, parents will also complete the ITSEA about their child.

4) STUDY EVALUATIONS AND MEASUREMENTS

a. Screening and Monitoring Evaluations and Measurements

i. Parent Adversity (ACE)

The 9 ACE questions query adults as to their exposure to 9 different adverse childhood experiences (economic hardship, domestic violence, parent mental health, discrimination, parent substance abuse, divorce, parent death, parent incarceration, and neighborhood violence) and are contained in the 2011-12 National Survey of Children's Health, a nationally representative telephone survey.

ii. Parent Health Literacy (SAHL)

The Short Assessment of Health Literacy (SAHL) is a validated measure of health literacy for English- and Spanish-speaking populations.

iii. Parent Depressive Symptoms (EPDS)

The Edinburgh Postnatal Depression Scale (EPDS) is a validated 10-item scale for postpartum depression symptoms with scores ≥ 9 having a sensitivity of 97% and specificity of 43% for major or minor depression.

iv. Reading Activity (StimQ)

The StimQ is an office measure of cognitive stimulation at home available in Spanish and English, and the Read subscale of the StimQ contains questions on the frequency of parent-child reading activity and the number and variety of books at home.²⁴ Psychometric analysis of the StimQ shows high internal consistency (Cronbach's Alpha=0.89) and test-retest reliability ($r=0.84$) and moderate correlation with the Bayley Scales of Infant Development ($r=0.52$, $p<0.001$).

We will also use a brief reading questionnaire (Appendix 12) about when participants began reading to their child and what influenced that decision.

v. Language Development (PLS)

The Preschool Language Scale-5th Edition (PLS) is a validated measure of expressive and receptive language function among children from birth through 7 years of age and is available in Spanish and English. The PLS has been standardized in over 1400 children nationally with a sensitivity of 0.83 and a specificity of 0.80 for the detection of language delay.

vi. Infant Toddler Social Emotional Assessment (ITSEA)

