The primary endpoint will be differences in PLS scores at 6 and 24 months of age.

b. Secondary Endpoints

Secondary endpoints will be the difference in StimQ scores at 6, 12, 18, and 24 months of age and the ITSEA scores at 18 and 24 months of age.

c. Statistical Methods

Summary statistics will be obtained, and differences between intervention and control groups will be assessed using intention-to-treat analysis. Cross-sectional differences in StimQ scores and PLS scores between intervention and control groups at the 6 and 24 month study visits and differences in ITSEA scores at 18 and 24 month study visits will be assessed using t-tests. To determine whether early literacy promotion is associated with greater language development, we will develop regression models using longitudinal data methods that adjust for correlation in PLS scores over time and for potential confounding by demographic characteristics. To explore whether early literacy promotion is associated with greater child socio-emotional development, we will develop regression models for scores at 18 and 24 months that adjust for potential confounding by demographic characteristics. To explore the impact of early literacy on healthcare utilization, the EHR will be reviewed to identify a subjects number of well visits and their vaccination history.

To determine whether parent adversity, health literacy, parenting stress, and/or depression modify the effects of early literacy promotion on language development, we will develop similar regression models using longitudinal data methods, but we will also fit interaction terms between study group and ACE score (≥ 4), SAHL (high or low), PSI score, and EPDS score (> 9) or PHQ-9 Score (> 4). To determine if parent-child reading activity mediates the association of intervention group assignment and language development, we will use mediation analysis with separate models regressing group assignment on language development, parent-child reading activity on group assignment, and group assignment on language development adjusted for parent-child reading activity.

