Assuming a power of 0.90, an alpha of 0.05, a 20% loss to follow-up over two years, and a clinically significant difference of 4 points or more on the expressive and receptive subscales of the PLS between groups, we estimate that we will need to recruit a total sample size of 120 eligible children (60 in each group) to participate in the study. All analyses will be conducted using Stata Statistical Software, version 13 (College Station, TX).

We will use NVIVO software to assist in data management for the semi-structured interviews. This software facilitates thematic coding, the assessment of inter-rater reliability, and correlation of themes with demographic variables. After detailed review of each transcript, we will develop a coding scheme and dictionary. We will use the constant comparative method in which newly collected data are compared with categories that have emerged from previously collected data. Through an iterative process, we will discuss the emerging themes as a team and revise the interview guide as needed to explore in depth themes arising from the data. If differences in coding arise, two members will discuss the data and negotiate to reach a consensus. If consensus cannot be reached a third member will decide the outcome. Once thematic saturation is reached, findings will be shared with participants at a follow up focus group after interviews have been conducted.

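### The primary PLS endpoint allows at least two, and possibly four, tests at a single alpha of 0.05, and no rule says which result decides Aim 1

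*Combined protocol and SAP*

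**What the plan says.** Section 5a (Primary Endpoint) reads: "The primary endpoint will be differences in PLS scores at 6 and 24 months of age". The Abstract, under Study Interventions and Measures, agrees: the group difference on the PLS "score at 6 and 24 months of age are the main outcomes". Neither place says whether the total score or the subscales are meant. The follow-up schedule does not settle it: "Children will complete measure of child expressive and receptive language development (Preschool Language Scale-V) at 6- and 24-month visits".

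Section 5c (Statistical Methods) gives two analyses of this endpoint:

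- T-tests of "Cross-sectional differences in StimQ scores and PLS scores between intervention and control groups at the 6 and 24 month study visits".
- For the question of greater language development, "regression models using longitudinal data methods that adjust for correlation in PLS scores over time and for potential confounding by demographic characteristics".

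The sample-size paragraph of section 5c describes the effect to be detected as "a clinically significant difference of 4 points or more on the expressive and receptive subscales of the PLS between groups". The remaining inputs are likewise single values: "Assuming a power of 0.90, an alpha of 0.05, a 20% loss to follow-up over two years". The result is 120 children, 60 per arm.

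No section ranks the scores, visits or analyses, says whether one or all results must be positive, or divides alpha.

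**The concern.** The stated 0.05 and 0.90 describe a single comparison, but the endpoint as defined contains several. With no deciding rule, the error rate and power of the primary conclusion are not those stated, and the same data could support opposite answers to Specific Aim 1.

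The design makes such disagreement realistic. The early programme covers visits before 6 months. Section 3.1 then says of the early arm, "Beginning with the 6-month well child visit, children in this arm will receive the standard ROR Program", and the control arm starts the same programme at that visit. An effect seen at 6 months and gone by 24 is therefore plausible, and that is where an any-one rule and an all-required rule part most sharply.

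**Working it through.** **Inputs from section 5c:** alpha 0.05, power 0.90, difference 4 points, 60 per arm, 20% loss over two years. **Assumed, because not stated:** two-sided tests; equal standardised effect on every comparison; the correlations given below; and, in the base case, the two-year loss already present at 6 months.

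**1. The plan's own figure.** Evaluable per arm: 60 × 0.80 = 48. No SD is given, so N cannot be reproduced directly. Solving n = 2·SD²·(1.960 + 1.282)²/4² at n = 48 gives SD = 4/(√(2/48) × 3.242) = 6.05 (5.98 with the t distribution). In the other direction, SD = 6 gives n = 2 × 36 × 10.51/16 = 47.3, rounded up to 48; 48/0.80 = 60 per arm, 120 in total. So N = 120 fits one two-sided comparison with an SD of about 6 and leaves nothing for further tests. The standardised effect giving exactly 90% power at 48 per arm is d = 0.6685.

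**2. Counting the tests.** Two visits on one score give two t-tests. Two visits by two subscales give four.

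**3. False-positive risk if any one t-test at 0.05 suffices.** This does not depend on the SD.

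- Two tests: 1 − 0.95² = 9.8% if independent; 7.8% at correlation 0.8.
- Four tests: 1 − 0.95⁴ = 18.5% if independent. By simulation, with correlations written as subscales/visits, 16% at 0.5/0.5, 15% at 0.7/0.5 and 13% at 0.8/0.7.

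**4. Power if all must succeed, each having 90% alone.**

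- Two tests: 0.9² = 81% if independent; 86% at correlation 0.8.
- Four tests: 0.9⁴ = 66% if independent; 73%, 75% and 79% at the same three correlation settings.
- If only 5% are lost by 6 months (60 × 0.95 = 57 per arm at that visit), all-four power is 72-82%.

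**5. Rules that do not lose power.**

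- Bonferroni on four tests, any one sufficing: alpha per test is 0.05/4 = 0.0125. Power for a given test falls to 76.5%, but the chance that at least one passes is 99.7%, 96.5%, 95% and 92% across the four settings (independent first) with equal effects. It is 95% down to 85% if the effect exists at 6 months only.
- One longitudinal contrast averaging both visits on one score: the effect becomes d/√((1 + r)/2), with r the between-visit correlation. At r = 0, 0.6685/0.707 = 0.945, power 99.6%. At r = 0.8, 0.6685/0.949 = 0.705, power about 93%. This assumes equal effects at both visits; averaging with a visit that shows no effect halves the mean difference and lowers power.

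**6. How far the rules can disagree.** With the planned effect on both subscales at 6 months and none at 24, any-one success at an unadjusted 0.05 occurs in 96-99% of simulated trials, and all-four success in about 1% or fewer.

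**The case against.** The best counter-argument is that section 5c already points to the longitudinal model as the primary analysis. Its stated purpose echoes Specific Aim 1, whereas the t-tests are introduced only as cross-sectional comparisons. A single averaged group effect on one score would be one test, and step 5 shows it would be well powered. This has weight and narrows the gap, but it does not close it. The text does not say that the model decides, which contrast it tests (average, 24 months, or change over time), or which PLS score it uses. Section 5a still defines the endpoint by differences at both visits.

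Three stronger readings are tempting and are not supported:

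- *The protocol states four primary comparisons.* It does not. The subscales appear only in the sample-size sentence; section 5a says PLS scores without specifying. Four comes from combining the two.
- *The trial is underpowered, or needs more children.* The 76.5% at alpha 0.0125 is power for one given test, not for the trial. Under Bonferroni with any-one success, trial power stays at about 92% or more with equal effects.
- *The power figures hold for any SD.* Only the false-positive figures do. The power figures take the plan's 90% as given, which at 48 per arm needs an SD of about 6. At SD 8, the normal approximation gives 69% for one test at 0.05.

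Nor does the plan's silence show any intention to choose the rule after seeing the data.

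**Conclusion.** The concern holds as a problem of definition and error control, and should be fixed before analysis. Run as written, with any one significant t-test counting, the plan carries about 8-10% false-positive risk on the narrowest t-test reading and 13-19% if both subscales count, against a stated 5%. If all are required, the stated 90% becomes about 81-86% or 66-79%.

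The ranges rest on assumed correlations: 0 to 0.8 for two tests; for four, 0 to 0.8 between subscales and 0 to 0.7 between visits. The power ranges also assume 90% for a single comparison, equal effects and 48 per arm at both visits. The documents do not show that a single comparison is underpowered. The unstated SD and sidedness are a separate reporting gap and not part of this error.

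**What to change.** In section 5a, name one PLS score and either one visit or one defined contrast from the longitudinal model as primary, say that this analysis decides Aim 1, and make the other PLS comparisons secondary. N = 120 with 90% power at 0.05 can then stay for that comparison.

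If several comparisons are to remain primary, state the success rule in advance (Holm or Bonferroni, a fixed testing order, or all required) and restate the power under it.

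The cost is two or three sentences in section 5, with no added participants or visits if one comparison is named. In exchange, the remaining PLS comparisons become secondary, or the stated power changes.

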7. SAFETY MANAGEMENT

7.1 Clinical Adverse Events

Clinical adverse events (AEs) will be monitored throughout the study. The main risks are disclosure of private health information (PHI) and study responses and discomfort with answering sensitive questions concerning childhood trauma or depressive symptoms.

7.2 Adverse Event Reporting

Since the study procedures are not greater than minimal risk, SAEs are not expected. If any unanticipated problems related to the research involving risks to subjects or others happen during the course of this study (including SAEs) they will be reported to the IRB in accordance with CHOP IRB SOP 408: Unanticipated Problems Involving Risks to Subjects. AEs that are not serious but that are notable and could involve risks to subjects will be summarized in narrative or other format and submitted to the IRB at the time of continuing review. We will query participants concerning any disclosures of PHI at each study visit. We will only query participants once concerning childhood trauma and depressive symptoms at the baseline visit.

8. STUDY ADMINISTRATION

8.1 Data Collection and Management

All records generated during this study will be kept confidential in accordance with Institutional policies and HIPAA on subject privacy. The Investigator and other site personnel will not use such data and records for any purpose other than conducting the study.

Unique identifiers will be created for each subject in the study. REDCap will be used to store the data. Since we are using REDCap, we will not need to maintain a Master List separate from the rest of the data. Participants' information will be stored in the REDCap database and configured

to export data without PHI. All de-identified records will be retained forever. Coded, de-identified data will be shared with the study sponsor.

Any paper copies of research instruments will be stored using the patient's ID code and will be kept in the department of General Pediatrics at The Children's Hospital of Philadelphia.

For the sub-study, a CHOP Sharedrive will be used to store all transcripts and digital recordings. Only study personal will have access to this server. All audio recordings will be transcribed by ADP a professional transcription service. They will not receive any personal health information and will be asked to remove all names while transcribing. The study team has an established business relationship in place with ADP. All audio recordings will be destroyed within three years of data analysis completion.

8.2 Confidentiality

All data and records generated during this study will be kept confidential in accordance with Institutional policies and HIPAA on subject privacy and that the Investigator and other site personnel will not use such data and records for any purpose other than conducting the study with the exception of mandatory reporting requirements for child maltreatment.

No identifiable data will be used for future study without first obtaining IRB approval. The research staff will obtain a data use agreement between the provider (the PI) of the data and any recipient researchers (including others at CHOP) before sharing a limited dataset (PHI limited to dates and zip codes).

8.3 Regulatory and Ethical Considerations

8.3.1 Data and Safety Monitoring Plan

Monitoring of adverse events, mainly disclosure of PHI from medical records and study assessment responses, will be ongoing during the intervention period until all data have been de-identified. Participants will be asked whether they know of any breaches of confidentiality at all contacts with subjects. All non-serious adverse events including disclosure of information will be reported to the CHOP IRB at the time of continuing review and to the funding agency annually. The PI will be responsible for overseeing the monitoring plan. Trained research assistants under the supervision of the Principal Investigator will conduct monitoring of data and safety twice annually.

8.3.2 Risk Assessment

There is minimal risk for harm to the participant in this study. Some information collected from the study participants on the study assessments is sensitive information and may cause the subjects discomfort, e.g. questions concerning childhood trauma or depressive symptoms. This

could include assessment of caregiver's suicidal ideations and a screening of caregiver's suicide risk in primary care flow. Also, question #9 on the PHQ-9 can indicate suicidal ideation or suicidal risk. The results of the screener and the PHQ-9 (Appendix 10) will be reviewed soon after completion (See Appendix 4). [name], PhD, is a co-investigator and child-psychologist who has expertise in early child development and measurement. She will serve as the licensed psychologist to contact if screener is positive or suicide risk is high. The follow-up plan is laid out in Appendix 13. This risk is considered minimal and no more than what is normally associated with being in a physician's or mental health practitioner's office. Furthermore, families incur a risk of disclosure of private health information to individuals not connected with this study. This could occur through inadvertent disclosure of PHI by research staff. This risk will be minimized by using the study identifier on all study instruments and the research database as well as storing identifying information in a separate place than study information.

Unique identifiers will be created for each subject in the study. REDCap will be used to store the data. Since we are using REDCap, we will not need to maintain a Master List separate from the rest of the data. Participants' information will be stored in the REDCap database and configured to export data without PHI. All de-identified records will be retained forever. Coded, de-identified data will be shared with the study sponsor.

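### Section 8.3.2 says identifying information is kept apart from study data, but the REDCap arrangement in 8.1 and 8.3.2 does not provide this; the transcription sentence and the disclosure-reporting rule also need repair

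*Combined protocol and SAP*

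**What the plan says.** **The risk.** Section 7.1: "The main risks are disclosure of private health information (PHI) and study responses", together with discomfort from sensitive questions. Section 8.3.1 also treats disclosure of PHI as the main event to be monitored.

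**The safeguards.** Section 8.3.2 gives two: a study identifier on the instruments and the research database, and "storing identifying information in a separate place than study information".

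**The data system.** The next paragraph of 8.3.2 says that, because REDCap is used, "we will not need to maintain a Master List separate from the rest of the data". Participant information goes into the REDCap database, which is set up so that exports omit PHI. Section 8.1 says the same, and adds that paper forms are filed under an ID code.

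**The interviews.** Section 8.1 says of the transcription firm: "They will not receive any personal health information and will be asked to remove all names while transcribing". It describes an established business relationship with the firm but gives no terms. On retention: "All audio recordings will be destroyed within three years of data analysis completion".

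**Reporting.** Section 7.2 opens one route with "If any unanticipated problems related to the research involving risks to subjects or others happen during the course of this study", and sends such events to the IRB under SOP 408. It sends adverse events that are notable but not serious to the IRB at continuing review. Section 8.3.1 says: "All non-serious adverse events including disclosure of information will be reported to the CHOP IRB at the time of continuing review", with a yearly report to the funder.

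**The concern.** The database holds sensitive answers: adverse childhood experiences, health literacy and postnatal depression at enrollment, then parenting stress and the PHQ-9, including its suicidality item, at 12, 18 and 24 months. Separate storage means that someone who reaches the answers does not thereby reach the names. If both are in one database, protection depends on access rights within that database and on how exports are configured. The IRB and the parents should be told which arrangement applies.

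The transcription sentence matters for the same reason. It reassures the reader that nothing identifying leaves the institution, and then gives an instruction that makes sense only if names may be on the recordings.

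The reporting text matters because 8.3.1 names disclosure as an example of an event for the slower route. A research assistant who found that names had been released with depression or suicidality answers, and who looked only at 8.3.1, could hold the report until continuing review.

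**Working it through.** There is no sample size, power or error rate behind this point and no figure in the plan to reproduce. The check sets the statements side by side.

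**1. Storage**

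| Statement | Section | Agrees with separate storage? |
|---|---|---|
| Identifying information is kept apart from study information | 8.3.2, first paragraph | This is the claim |
| No master list is kept apart from the other data | 8.3.2, next paragraph; 8.1 | No |
| Participant information is in the REDCap database | 8.3.2; 8.1 | No |
| Exports are configured to leave out PHI | 8.3.2; 8.1 | No: a setting that drops PHI on export implies that the database holds it |
| Unique study identifiers; paper forms under an ID code | 8.3.2; 8.1 | Neutral: this supports the other safeguard |

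The separation claim and the REDCap description cannot both stand as written. The study-identifier safeguard is not contradicted, although an identifier protects less when the names are in the same database.

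**2. Transcription.** The sentence has two halves. If the firm received nothing identifying, it would have no names to remove. Since it is asked to remove names, the recordings it receives may contain them. A name alone may not count as health information, so the first half could be true in a narrow sense, but it does not tell the reader that identifiers may leave the institution.

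**3. Reporting**

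| Type of event | 7.2 | 8.3.1 |
|---|---|---|
| Unanticipated problem involving risk, including an SAE | IRB under SOP 408 | Not addressed |
| Non-serious event | IRB at continuing review | IRB at continuing review; funder yearly |
| Disclosure of information | Not classified | Listed among non-serious events |

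The sections agree on non-serious events, and 8.3.1 does not cancel the SOP 408 route. What is missing is a rule for when a disclosure moves from the second row to the first.

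**4. Detection.** Section 7.2 has participants queried at each study visit (enrollment and 6, 12, 18 and 24 months, so 5 visits). Section 8.3.1 says at all contacts. The wider statement contains the narrower, so there is no contradiction. Section 8.3.1 also continues monitoring until all data are de-identified and provides for monitoring of data and safety twice a year.

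**5. Size.** Storage: all 120 dyads (120 × 2 = 240 participants, section 3.3.2). Recordings: at most 30 parents, or 30/120 = 25% of those enrolled. Reporting delay: the documents do not give the interval between continuing reviews. A disclosure held for continuing review could wait anything from no time to one full interval. If review is yearly, which is an assumption, that is 0 to about 12 months.

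**The case against.** The strongest case against is that this is a wording problem in a plan with several working controls: study identifiers, exports without PHI, recordings on a server restricted to study staff, data use agreements for sharing a limited dataset (8.2), participant queries, twice-yearly monitoring and IRB reporting. All of these stand. A reader might infer that the main risk goes uncontrolled, undetected or unreported. The documents do not support that.

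Three narrower inferences also fail:

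- **That the minimal-risk rating depends on separate storage.** In 8.3.2 the rating follows the text on discomfort and suicidality and comes before disclosure is raised. Section 8.3.4 calls the risks minimal and then says that protections reduce them further.
- **That a disclosure after the 24-month visit would go unnoticed because detection relies on visit queries.** Section 8.3.1 provides more than visit queries. The three-year limit on recordings is a maximum, and nothing says recordings fall outside the monitored data.
- **That 7.2 and 8.3.1 give conflicting routes.** They are tiers for different kinds of event.

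It can also be said that separate storage might mean a restricted form or restricted fields inside REDCap. That is possible, but neither section says so, and both say that nothing separate is needed.

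Finally, SOP 408 is not in the documents and may itself classify privacy breaches. If it does, the repair to 8.3.1 is a cross-reference, but 8.3.1 as it stands still directs staff to continuing review.

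**Conclusion.** The point holds in a limited form. One contradiction is clear: the separate-storage safeguard in 8.3.2 is not the arrangement described in the next paragraph of 8.3.2 and in 8.1. One sentence in 8.1, on the transcription firm, undercuts itself. One gap exists: nothing says when a disclosure becomes an SOP 408 matter.

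The storage point covers every enrolled dyad, and the transcription point at most a quarter of the parents. The possible reporting delay cannot be sized from the documents; about 12 months is the upper end only if continuing review is yearly and staff overlook 7.2. That names are on the recordings is inferred from the instruction to remove them.

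Allocation, endpoints, analysis and interpretation are untouched. The changes are still worth making, because they concern the first of the protocol's own main risks and cost little.

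**What to change.** 1. **Reconcile 8.1 and 8.3.2.** Either hold names, contact data and the linking key in a separate restricted REDCap project joined by study ID, or remove the separation claim and describe the controls actually in place (access rights, exports without PHI). The first option keeps the stated safeguard; the second needs wording only.
2. **Correct the transcription sentence in 8.1.** Say that recordings may contain names, confirm with the firm the terms under which it handles them (the protocol states none), and have interviewers avoid names on tape.
3. **Amend 8.3.1.** A PHI disclosure that meets the SOP 408 definition is reported under SOP 408 when found; only the remainder waits for continuing review. Add the matching cross-reference in 7.2, and use the same query frequency in both sections.

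The cost is a protocol amendment, a check of the terms with the transcription firm and, under the first option in item 1, one REDCap configuration change. The downside is slightly more database administration.
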